No adjustment to the significance level for testing of subgroups will be made since all these subgroup analyses will be considered exploratory and may only be supportive of the primary analysis of PFS.

The presence of quantitative interactions will be assessed by means of an overall global interaction test. This will be performed in the overall population by comparing the fit of a Cox proportional hazards model including treatment, all covariates (stratification factors), and all covariate-by-treatment interaction terms, with one that excludes the interaction terms and will be assessed at the 2-sided 10% significance level. If the fit of the model is not significantly improved then it will be concluded that overall the treatment effect is consistent across the subgroups.

If the global interaction test is found to be statistically significant, an attempt to determine the cause and type of interaction will be made. Stepwise backwards selection will be performed on the saturated model, whereby (using a 10% level throughout) the least significant interaction terms are removed one-by-one and any newly significant interactions re-included until a final model is reached where all included interactions are significant and all excluded interactions are non-significant. Throughout this process all main effects will be included in the model regardless of whether the corresponding interaction term is still present. This approach will identify the factors that independently alter the treatment effect and prevent identification of multiple correlated interactions.

Any quantitative interactions identified using this procedure will then be tested to rule out any qualitative interaction using the approach [Gail and Simon 1985](#).

A further analysis of PFS (using Investigator assessed RECIST) may be performed at the time of the OS analyses, if requested by Health authorities.

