12.3 Determination of sample size

The sample size for this study was selected to be consistent with the research hypothesis as described in Section 1.

The primary endpoint of the study is PFS. In total 230 PFS events in the study would have 90% power to show statistically significant PFS at the one-sided 2.5% level if the assumed true treatment effect were HR 0.635; this translates to an approximate 2 month clinically relevant improvement in median PFS over an assumed 4 month median PFS on chemotherapy assuming PFS is exponentially distributed.

Approximately 310 patients will be recruited (2:1 ratio) so that data maturity for the PFS analysis is approximately 75%.

It is estimated that the study recruitment period will be approximately 22 months and that 230 progression events will have occurred approximately 27 months after the first patient is randomised in the study. This will be the primary analysis of PFS. No further analyses of PFS are planned beyond this point unless requested by Health Authorities.

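### Section 12.2.2 promises that stepwise selection will identify the factors that independently modify the treatment effect; at 230 events the procedure does not have that property

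*Protocol*

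**What the plan says.** Protocol Section 12.2.2 sets out a chain of steps for PFS.

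- **Global test.** A Cox model "including treatment, all covariates (stratification factors), and all covariate-by-treatment interaction terms" is compared with the same model without interactions, at a two-sided 10% level. The stratification factors are prior chemotherapy for metastatic disease, ER/PgR status and prior platinum for breast cancer.
- **Selection.** Only if that test is significant, backward selection runs at 10% with all main effects kept: "the least significant interaction terms are removed one-by-one and any newly significant interactions re-included until a final model is reached".
- **Claim.** "This approach will identify the factors that independently alter the treatment effect and prevent identification of multiple correlated interactions".
- **Next step.** Interactions found this way are tested for a qualitative interaction by the Gail-Simon method.

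The same section calls the subgroup analyses exploratory and supportive only. Subgroup HRs on the forest plot come from separate single-factor interaction models and are shown whether or not a factor is selected, subject to the 20-event minimum.

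Section 12.3 sizes the trial for the overall effect, with an HR of 0.635 taken as the truth: "In total 230 PFS events in the study would have 90% power to show statistically significant PFS at the one-sided 2.5% level". No power or error rate for an interaction is given there.

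**The concern.** The claim about what selection achieves is unqualified. Stepwise selection keeps terms that pass a threshold in one data set. It does not establish which factors truly modify the effect, least of all when each interaction is estimated with half the precision of the main effect and the candidates may overlap. Terms kept because they passed also tend to look larger than they are.

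Two things depend on the outcome: which factor is named as altering the effect of olaparib, and which factors reach the Gail-Simon test. A true modifier that is dropped is never checked for a qualitative interaction.

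**Working it through.** **1. The protocol's own figure.** Inputs from Section 12.3: HR 0.635, one-sided 2.5%, 90% power, 2:1 allocation.

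Events = (1.960 + 1.282)² / [(2/3)(1/3)(ln 0.635)²] = 10.51 / (0.2222 × 0.2062) = 229.3, so 230. Power at 230 events is 90.1%. The stated figure is reproduced.

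**2. Precision of an interaction.** For a binary factor with prevalence p, SE of the log HR ratio ≈ 1/√[230 × (2/9) × p(1−p)].

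- Overall effect: 1/√51.1 = 0.14.
- Interaction, p = 0.5: 1/√12.8 = 0.28, twice as large.
- Interaction, p = 0.3: 1/√10.7 = 0.31.

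Power of one 10% test is Φ(|ln ratio|/SE − 1.645). For ratios 0.5 / 0.6 / 0.7 it is 80% / 57% / 36% at p = 0.5 and 73% / 51% / 32% at p = 0.3.

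**3. Simulation of the stated procedure.** 310 patients 2:1, exponential PFS, average HR about 0.635, 22-month uniform accrual, cut at the 230th event. Three-df likelihood-ratio test at 10%, then backward elimination at 10% with re-entry. 600 to 1,500 trials per scenario.

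*Assumption set A (not in the protocol):* prior chemotherapy 70%; ER/PgR positive 50%; prior platinum 40% of those with and 8% of those without prior chemotherapy; main-effect HRs 1.3, 0.85 and 1.3. Ranges are over repeated runs. All columns after the second are conditional on a significant global test.

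| Truth | Global test significant | Exactly right | False factor named | True factor missed | Mean retained ratio |
|---|---|---|---|---|---|
| No interaction | 11–13% | – | practically all | – | 2.0 |
| Platinum, 1.5 | 30% | 49–57% | 42–51% | 19–20% | 2.16–2.22 |
| Platinum, 2.0 | – | 73–75% | – | 5% | 2.44 |
| Chemotherapy and platinum, 1.6 each | 68% | – | – | at least one in 75–81% | 2.2–2.3 |

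In the no-interaction row, one run of only 600 trials gave 8%. Simulation error in the second row: 0.30 × 1,500 = 450 trials reach selection, so the SE of 57% is √(0.57 × 0.43/450) = 2.3 points.

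*Assumption set B:* prevalences 70/50/30%, latent correlation 0 to 0.3, no main effects, ER/PgR status the one true modifier.

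| True ratio | Exactly right | False factor named | True factor dropped | Mean ratio when kept |
|---|---|---|---|---|
| 0.5 | 73–74% | 26–28% | 3–4% | 0.42–0.43 |
| 0.6 | 65–67% | 33–35% | 9–11% | 0.45 |
| 0.7 | 50–52% | 48–49% | 20–21% | 0.48 |

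At correlation 0.6 and ratio 0.6, selection is exactly right in 62%. At ratio 0.4 (correlation 0) it is right in 78%.

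**4. Where the exaggeration arises (set A).** With one modifier of 1.5, the full three-interaction model, read only when the global test is significant, averages 1.98–2.01, against 2.16–2.22 after selection. So (1.98 − 1.5)/(2.16 − 1.5) = 73% of the excess is already present before selection. With two modifiers of 1.6 the figures are 1.75–1.80 and 2.2–2.3, and selection adds most of it. Reported regardless of the global test, the full model averages 1.49 for a true 1.5 and 1.62 for a true 1.6.

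**5. The word independently.** *BRCA* type is a listed subgroup but not a candidate in the selection model. Section 1.1.1 gives about 70% of *BRCA1* and 20% of *BRCA2* tumours as triple negative, and a 60/40 split in an earlier olaparib study. If *BRCA* type were the true modifier (ratio 0.5–0.6), the global test would be significant in 18–23% of trials, and hormone-receptor status would be named in 61–74% of those.

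**The case against.** The strongest reply is that this is a gated, exploratory step on three pre-specified factors, and that one over-confident sentence needs only softening. Much of that stands. With no interaction, false naming is close to the nominal 10%. That nearly every trial reaching selection then names a factor follows almost automatically from conditioning on a significant global test. Most misses also reflect low power: with two modifiers of 1.6, at least one true modifier's 95% CI in the full model includes 1 in 91% of trials with a significant global test. No reporting format cures that.

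Several stronger readings are tempting but unsupported:

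- *Inflated estimates are reported or passed to Gail-Simon.* The protocol says neither. It sends the identified interactions for testing without saying which estimates are used. Exaggeration applies to any effect highlighted because it was selected.
- *The choice between overlapping factors is largely chance.* With a true ratio of 1.5 the true factor is kept in about 80% of trials that reach selection, and at 2.0 in 95%.
- *Avoiding correlated interactions must discard one of two true modifiers.* Both stay if both are significant jointly, and re-entry is allowed.
- *The trial would declare which patients benefit.* The text speaks of an attempt to find the cause and type of interaction.

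The overlap between prior chemotherapy and platinum is itself assumed. The platinum factor is not limited to metastatic use, so overlap may be smaller; with ER/PgR status and platinum as the two modifiers, at least one is dropped in 63%.

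The exploratory label does not, however, qualify the promise that factors will be identified, and selection still decides which factors reach Gail-Simon.

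**Conclusion.** The point holds. The procedure is fully specified in the protocol, and the property claimed for it is one it does not have at 230 events. Once selection starts, it is wrong in roughly 25–50% of trials with one true modifier of 1.5–2.0, and it drops at least one of two overlapping modifiers of 1.6 in roughly 75–80%. Selected effects are exaggerated, partly by the global test and partly by selection.

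The percentages rest on assumed prevalences, overlap and interaction sizes; the direction did not change over the range tried. The primary PFS test, the testing hierarchy and the sample size are unaffected. The weight is low to moderate: worth changing because it alters which factors are named and tested further.

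**What to change.** In Section 12.2.2, and in the SAP if it repeats the text:

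1. Delete the stepwise selection and the sentence on what it will identify.
2. Report all three treatment-by-factor HR ratios with 95% CIs from the single full interaction model, whether or not the global test is significant, labelled hypothesis-generating. Reporting them only after a significant global test would keep that part of the exaggeration.
3. If the global test is significant, apply the Gail-Simon test to all three stratification factors, not only to selected ones.

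The cost is wording and somewhat less programming. The downside is that no single factor is named as the source of an interaction.

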12.2.2.1 Sensitivity Analyses for Primary Endpoint

As a sensitivity analysis to the primary endpoint of PFS, the primary analysis will be repeated excluding any patients who did not have a *gBRCA* mutation status confirmed by the Myriad test. The same methodology and model will be used and the HR and associated 95% CI from a Cox Proportional Hazards model will be reported.

Sensitivity analyses will be performed to assess the possible presence of time-assessment bias (i.e., differential assessment times between treatment groups).

Summary statistics for the number of weeks between the time of progression and the last evaluable RECIST assessment prior to progression will be presented for each treatment group.

(a) Evaluation-Time bias

Sensitivity analyses will be performed to assess possible evaluation-time bias that may be introduced if scans are not performed at the protocol-scheduled time points. The midpoint between the time of progression and the previous evaluable RECIST assessment will be analysed using a stratified log rank test, as described for the primary analysis of PFS. This approach has been shown to be robust to even highly asymmetric assessment schedules ([Sun and Chen 2010](#)). This approach will use the BICR RECIST assessments.

(b) Attrition bias

Attrition bias will be assessed by repeating the primary PFS analysis except that the actual PFS event times, rather than the censored times, of patients who progressed or died in the absence of progression immediately following two, or more, non-evaluable tumour assessments will be included. In addition, patients who take subsequent therapy prior to progression or death will be censored at their last evaluable assessment prior to taking the subsequent therapy.

Additionally a Kaplan-Meier plot of the time to censoring where the censoring indicator of the primary PFS analysis is reversed will be presented.

(c) Ascertainment bias

A stratified log-rank test will be repeated using the programmatically derived RECIST using Investigator assessed PFS. The HR and 95% Confidence Interval will be presented.

If there is an important discrepancy between the primary analysis using BICR assessments and this sensitivity analysis using Investigator assessments, then the proportion of patients with site but no central confirmation of progression will be summarised. The approach of imputing an event at the next visit in the central review analysis may help inform the most likely HR value, but only if an important discrepancy exists.

Disagreements between investigator and central reviews of RECIST progression will be presented for each treatment group. The summary will include the early discrepancy rate which is the frequency of investigator review progressions declared before the BICR as a proportion of all investigator review progressions and the late discrepancy rate which is the frequency of investigator review progressions declared after the BICR as a proportion of all discrepancies.

(d) Deviation bias (if meaningful to do)

As a sensitivity analysis to the primary endpoint of PFS, an analysis excluding patients with deviations that may affect the efficacy of the trial therapy will be performed if > 10% of patients:

- did not have the intended disease or indication or
- did not receive any randomised therapy

A stratified log-rank test will be repeated using the BICR RECIST data, using the same ties and stratification factors as described for the primary analysis of PFS. The HR and 95% CI will be presented.

As a supportive analysis, time to first subsequent therapy or death (TFST) will be analysed using the same methodology and model. The HR for the treatment effect together with its 95% CI will be presented. In addition, a Kaplan Meier plot of time to start of subsequent therapy or death will be presented by treatment arm. The time between progression and starting subsequent therapy will also be assessed. No multiplicity adjustment will be applied as this is viewed as a supportive endpoint.

A summary table of first subsequent therapies by treatment arm will be provided.

12.2.3 Analysis of secondary endpoints

12.2.3.1 Analysis of PFS2 endpoint

An initial PFS2 analysis will be performed at the same time as the primary analysis of PFS and will use the same methodology and model. A further analysis of PFS2 will be performed when the OS data are approximately 60% mature. A Kaplan-Meier plot of PFS2 will be provided along with median PFS2 for each treatment. The number and percentage of patients experiencing a PFS2 event and the type of progression (objective radiological progression, symptomatic progression or death) will be summarised by treatment arm.

As a supportive analysis, time to start of second subsequent therapy or death (TSST) will be analysed using the same methodology and model. The HR for the treatment effect together with its 95% CI will be presented. In addition, a Kaplan Meier plot of time to start of second subsequent therapy or death will be presented by treatment arm. No multiplicity adjustment will be applied as this is viewed as a supportive endpoint.

A summary table of second subsequent therapies by treatment arm will be provided.

12.2.3.2 Analysis of OS endpoint

OS data will be analysed at the time of the primary analysis of PFS and will use the same methodology and model (provided there are sufficient events available for a meaningful analysis [> 20 deaths], if not descriptive summaries will be provided). A further analysis of OS will be performed when the OS data are approximately 60% mature.

The sensitivity analysis outlined for 12.2.2.1 will not be repeated for OS with the exception of a Kaplan-Meier plot of the time to censoring where the censoring indicator of the primary OS is reversed.

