- Eribulin mesylate 1.4 mg/m² or Eribulin (active substance) 1.23mg/m² IV Day 1 and Day 8, repeat every 21 days

Duration of treatment

Patients will be randomised (using an IVRS/IWRS) in a 2:1 ratio to the treatments as specified below:

- Olaparib tablets po. 300 mg twice daily
- Physician's choice of chemotherapy (capecitabine, vinorelbine or eribulin)

Patients should continue to receive study treatment until objective radiological disease progression as per RECIST 1.1 as assessed by the investigator or unacceptable toxicity and they do not meet any other discontinuation criteria. Patients who are determined to have progressed according to RECIST 1.1 criteria by the Investigator will have scans centrally reviewed for confirmation of objective disease progression. If disease progression is not confirmed at central review an additional RECIST assessment will be requested at the next scheduled RECIST visit. Once patients have been discontinued from study treatment, other treatment options will be at the discretion of the investigator. Within this study, patients on chemotherapy will not be provided olaparib post discontinuation of study treatment.

All patients should continue RECIST assessments until documented evidence of objective radiological progression in accordance with RECIST 1.1, irrespective of treatment decisions

(i.e RECIST follow up until progression even if a patient discontinues study treatment prior to progression and/or receives a subsequent therapy prior to progression).

Outcome variable(s):

- Primary outcome variable
 - Progression Free Survival by BICR using RECIST 1.1.
- Safety outcome variables
 - Adverse Events (AE), physical examination, vital signs including blood pressure (BP), pulse, electrocardiogram (ECG) and laboratory findings including clinical chemistry and haematology
- Secondary outcome variables
 - Overall Survival
 - Time from randomisation to second progression, defined as objective radiological or symptomatic progression or death (PFS2)
 - Objective Response Rate by BICR using RECIST 1.1
 - PFS, PFS2 and OS based on patients with *gBRCA* mutations confirmed by the central test (only required if population differs from the ITT population)
 - Adjusted mean change from baseline in global QoL score from the EORTC-QLQ-C30 questionnaire
 - Pharmacokinetic sampling
- Exploratory outcome variables
 - Potential retrospective biomarker research

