2.2 Secondary objectives

The secondary objectives of this study are:

1. To compare the efficacy of single agent olaparib versus physician's choice chemotherapy (capecitabine, vinorelbine or eribulin) by assessment of overall survival, time to second progression or death (PFS2) and objective response rate (ORR) using BICR data assessed by RECIST 1.1.
2. To assess the effect of olaparib on the Health-related Quality of Life (HRQoL) as measured by EORTC QLQ-C30 global QoL scale.
3. To assess efficacy of olaparib in patients identified as having a deleterious or suspected deleterious variant in either of the *BRCA* genes using variants identified with current and future *BRCA* mutation assays (gene sequencing and large rearrangement analysis).
4. To determine the exposure to olaparib in patients receiving olaparib monotherapy

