12.2 Methods of statistical analyses

The treatment comparison is olaparib 300 mg bid vs physician's choice of chemotherapy.

Results of all statistical analysis will be presented using a 95% confidence interval and 2-sided p-value.

The following table details which endpoints are to be subject to formal statistical analysis, together with pre-planned sensitivity analyses making clear which analysis is regarded as primary for that endpoint

Table 10 Formal Statistical Analyses to be Conducted and Pre-Planned Sensitivity Analyses

Endpoints Analysed	Notes
PFS (Time from randomisation to first progression or death)	Primary analysis stratified log-rank test using BICR data
	Sensitivity/supportive analyses ^a :
	1) Evaluation time bias analysis; stratified log-rank test using BICR data
	2) Attrition bias analysis (using alternative censoring rules); stratified log-rank test using BICR data
	3) Ascertainment bias analysis; stratified log-rank test using Investigator data
	4) Deviation bias (if meaningful to do); stratified log-rank test using BICR data
	5) Stratified log rank test of time from randomisation to first subsequent therapy or death 6) stratified log rank test using BICR data in randomised patients confirmed as BRCA mutation positive by central Myraid test (if applicable)
Overall Survival (Time from randomisation to death due to any cause)	Primary analysis: stratified log-rank test Supportive analysis: KM plot of time to censoring for OS
PFS2 (Time from randomisation to second progression or death)	Primary analysis: Stratified log rank test based on investigator assessment of second progression Supportive analysis: Stratified log rank test of time from randomisation to second subsequent therapy or death
Objective Response Rate (Number of patients who have a CR or PR determined using RECIST 1.1 criteria divided by the number of patients with measurable disease.)	Primary: ORR per treatment arm (descriptive only) based on BICR data Supportive: ORR per treatment arm (descriptive only) based on investigator assessment

Table 10 Formal Statistical Analyses to be Conducted and Pre-Planned Sensitivity Analyses

Endpoints Analysed	Notes
Adjusted mean change from baseline in global QoL score from the EORTC QLQ-C30 questionnaire	Primary analysis: mixed model for repeated measures (MMRM) analysis of all of the post-baseline scores for each visit

^a See Section 12.2.2.1 for further details

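### OS in centrally confirmed gBRCA patients is a listed secondary outcome, but section 12.2.3.2 as worded excludes its analysis

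*Protocol*

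**What the plan says.** **Objective.** Secondary objective 3 (section 2.2) begins "To assess efficacy of olaparib in patients identified as having a deleterious or suspected deleterious variant in either of the *BRCA* genes", with variants identified by current and future assays. It speaks of efficacy in general and names no endpoint.

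**Outcome.** The synopsis, under secondary outcome variables, does name endpoints: "PFS, PFS2 and OS based on patients with *gBRCA* mutations confirmed by the central test". A parenthesis makes this necessary only where the confirmed population is not the same as ITT.

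**Analysis of PFS.** Section 12.2.2.1 opens with this population: "the primary analysis will be repeated excluding any patients who did not have a *gBRCA* mutation status confirmed by the Myriad test". Table 10 repeats it as item 6 of the PFS row: "stratified log rank test using BICR data in randomised patients confirmed as" mutation positive by the central test, if applicable.

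**Analysis of OS.** Section 12.2.3.2 says: "The sensitivity analysis outlined for 12.2.2.1 will not be repeated for OS with the exception of a Kaplan-Meier plot of the time to censoring". The OS row of Table 10 gives the stratified log-rank test as primary and then only "Supportive analysis: KM plot of time to censoring for OS".

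**Analysis of PFS2.** Section 12.2.3.1 and the PFS2 row of Table 10 give the main analysis and the supportive analysis of time to second subsequent therapy or death. The confirmed population is not mentioned.

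**Analysis sets.** Table 9 assigns OS and PFS2 to the FAS (ITT). Section 12.1 defines no centrally confirmed set.

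**The concern.** The synopsis and section 12 give opposite instructions for the same OS outcome: one lists it, the other excludes the only analysis in section 12 that uses its population. This is not detail left for a statistical analysis plan to supply. A plan that includes OS in confirmed patients departs from section 12.2.3.2; one that leaves it out fails the synopsis.

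At stake is whether the trial report can show that an OS result seen in all randomised patients also holds in those the central test identifies. Patients can be randomised on an earlier local result, so the two populations need not coincide.

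**Working it through.** The point rests on the text, so the check sets the sections side by side.

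**Step 1. Does the exclusion reach this analysis?** Section 12.2.2.1 contains the confirmed-gBRCA analysis (its first paragraph, which itself calls it a sensitivity analysis), then evaluation-time, attrition, ascertainment and deviation bias, and the supportive analysis of time to first subsequent therapy or death. Section 12.2.3.2 refers to 12.2.2.1 as a whole and makes one exception, the reversed-censoring Kaplan-Meier plot. The confirmed-gBRCA analysis is not excepted, so it is excluded for OS.

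**Step 2. Is it restored elsewhere?** Coverage of the confirmed-gBRCA population by endpoint:

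| Endpoint | Synopsis outcome list | Text of section 12.2 | Table 10 |
|---|---|---|---|
| PFS | listed | specified (12.2.2.1) | item 6 of the PFS row |
| OS | listed | excluded (12.2.3.2) | absent |
| PFS2 | listed | not mentioned (12.2.3.1) | absent |

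Section 12.2.5 adds only a descriptive summary of BRCA status by the central test. Of three listed endpoints, one has an analysis, one is excluded and one is omitted.

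**Step 3. Can the condition be met?** Patients of unknown status need a positive Myriad result before randomisation, so they are confirmed on entry. Patients with a known mutation may be randomised on that result, and the central test follows. Under section 6.6.2.1 such a patient may remain in the study if the central test does not show a deleterious or suspected deleterious mutation. The FAS keeps all randomised patients (section 12.1.1). One such patient is enough for the confirmed population to differ from ITT.

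**Step 4. Would the OS analysis be too imprecise to be worth doing?** The protocol gives no proportion of unconfirmed patients. As an assumption only, take 5% to 10% of the 310 randomised, with OS events lost in the same proportion from the approximately 190 planned for the final analysis. With 2:1 randomisation, SE(log HR) is approximately sqrt(1 / (d × 2/3 × 1/3)) = sqrt(4.5/d), where d is the number of events.

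| Not confirmed (assumed) | Patients excluded | OS events left | SE(log HR) |
|---|---|---|---|
| none (ITT) | 0 | 190 | sqrt(4.5/190) = 0.154 |
| 5% | 0.05 × 310 = 15.5, about 16 | 0.95 × 190 = 180.5, about 181 | sqrt(4.5/181) = 0.158 |
| 10% | 0.10 × 310 = 31 | 0.90 × 190 = 171 | sqrt(4.5/171) = 0.162 |

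Over this range the analysis is nearly as precise as ITT, so precision is no reason to drop it. The figures show feasibility; they do not measure harm.

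**The case against.** The strongest reply is that the sentence in 12.2.3.2 was not aimed at this analysis. Most of 12.2.2.1 concerns how progression is assessed, which has little meaning for OS, and the section is headed as sensitivity analyses for the primary endpoint. OS in confirmed patients is a secondary outcome in its own right, so a looser reading could keep both texts. That is probably what was meant. But the sentence covers the whole section and lists its exception, and the OS row of Table 10 agrees with the literal reading. An over-broad cross-reference still needs correcting.

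A second reply is that the consequence is conditional and may be small. This stands. If every patient is centrally confirmed, nothing is lost. With 5% to 10% unconfirmed, 90% to 95% of the OS events would be shared with ITT, and the extra result would usually sit close to the ITT estimate.

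A third is that the companion-diagnostic rationale in section 3.1 concerns the collection of blood samples and does not call for OS in confirmed patients. This also stands. The point rests on the listed outcome, not on that rationale.

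A reader might infer that PFS2 is ruled out too. The documents do not support this: the exclusion names OS only, section 12.2.3.1 carries over the PFS methodology and model, and an analysis plan could supply the PFS2 analysis without contradicting anything. For PFS2 there is an omission, made visible because Table 10 sets out to list the pre-planned sensitivity analyses and shows this one under PFS alone.

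**Conclusion.** The inconsistency is real for OS. The synopsis lists OS in centrally confirmed gBRCA patients as a secondary outcome; section 12.2.3.2, supported by Table 10, excludes its analysis. If section 12 is followed as written, that outcome goes unanalysed whenever at least one randomised patient is not centrally confirmed. PFS2 is a lesser gap in consistency.

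Two further inferences should not be drawn:

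- **That OS in this population would be added only once the ITT OS results are known.** The synopsis already pre-specifies the outcome, and section 12.1 plans the statistical analysis plan before the first patient enters, so the conflict can be settled in advance.
- **That secondary objective 3 is failed.** It asks for efficacy without naming OS or PFS2, and PFS is analysed in that population. What is unmet is the synopsis outcome line.

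The size in practice depends on an unknown discordance rate; the 5% to 10% used above is an assumption. The primary PFS analysis, the ITT analyses of OS and PFS2 and type I error control are untouched. This should be corrected, but it does not threaten the trial's main conclusions.

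**What to change.** In section 12.2.3.2, add the centrally confirmed gBRCA analysis to the exceptions, beside the time-to-censoring plot. In Table 10, add to the OS row a stratified log-rank test in randomised patients confirmed by the central test, to be done if that population differs from ITT and outside the multiple testing procedure. For consistency with the synopsis, add the same entry to the PFS2 row.

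Restricting the synopsis outcome to PFS, with a stated reason, would also remove the contradiction, but it would give up a listed secondary outcome that can be analysed from data already collected.

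The cost is a wording change and a few more tables, with no new patients, visits or data. The downside is some additional supportive results without alpha control, which should be labelled as such.
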